8.4.3 Analysis of the Secondary Efficacy Endpoint

The study will aim to determine whether treatment administration can increase the quantity and quality of circulating antigen-specific T-cells, by measuring the reactivity of circulating cells against the immunizing peptides in Elispot and 41BB upregulation assays. The comparisons will be done using descriptive statistics, without formal statistical testing required.

8.4.4 Safety Analyses

Safety will be monitored by identifying the type and severity of any adverse events. The fraction of patients who experience a DLT will be identified at a given dose level, with information reported about the number and grade of each type of DLT identified.

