3.1.4 Dose-Limiting Toxicity

The dose-limiting toxicity (DLT) evaluation period for determination of the maximum tolerated vaccine dose (MTD) will occur during the 21 days after the first vaccination for each patient. A DLT is defined as follows: All grade 3 or greater toxicities related to the mRNA vaccine, with the exception of:

- Grade 3 fever
- Grade 3 pruritus/itching
- Grade 3 fatigue
- Grade 3 metabolic laboratory abnormalities without significant clinical sequela that resolve to grade 2 or less within 7 days.
- Grade 3 autoimmune toxicity that resolves to grade 2 or less within 7 days.
- Events that are clearly related to the patient's disease.
- 3.1.5 Phase I Dose Escalation

Subjects will receive their assigned dose level of NCI-4650 as IM injections on Days 0, 14, 28, and 42. The maximum dose of mRNA vaccine for each dose level will be:

Dose Level	vel NCI-4650, mRNA Vaccine Dose	
Level 1	0.04 mg (0.0006 mg/kg based on a 70-kg subject)	
Level 2	0.13 mg (0.0019 mg/kg based on a 70-kg subject)	
Level 3	0.39 mg (0.0056 mg/kg based on a 70-kg subject)	

Moderna is the sponsor of a dose escalation trial utilizing a nearly identical vaccine (mRNA-4157) as the mRNA vaccine used in this protocol (NCI-4650). The dose escalation in both protocols is the same (0.04 mg, 0.13 mg, and 0.39 mg). As indicated in the Moderna Safety Review Committee Dose Level Approval Form dated 21 December 2017, the Moderna Medical Monitor noted that for the three patients enrolled on Dose Level 1 (Part A) in the Moderna trial (0.04 mg mRNA-4157 monotherapy), no DLTs were experienced and the only AEs experienced were grade 1 injection site soreness, which is expected for the vaccine. As a result, Dose Level 1 was declared safe and tolerated. For this trial, because Dose Level 1 was shown to be safe and tolerated, the first two patients were enrolled on Dose Level 2. No DLTs were experienced and the only AEs experienced were grade 1 and 2 related events.

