3.8.1 Criteria for Removal from Protocol Therapy

Patients will be taken off treatment for the following:

- Completion of second follow-up evaluation
- Grade 3 or 4 toxicity due to the vaccine, excluding those known events such as local injection site reactions, skin rash, pruritus, fatigue, fever and local adenopathy.
- Progression of disease
- Patient requests to be withdrawn from protocol therapy
- Investigator discretion
- Positive pregnancy test

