6 DATA COLLECTION AND EVALUATION

6.1 DATA COLLECTION

The PI will be responsible for overseeing entry of data into an in-house password-protected electronic system (C3D) and ensuring data accuracy, consistency and timeliness. The PI, associate investigators (AI), research nurses, and/or a contracted data manager will assist with the data management efforts. All data obtained during the conduct of the protocol will be kept in secure network drives or in approved alternative sites that comply with NIH security standards.

Primary and final analyzed data will have identifiers so that research data can be attributed to an individual human subject participant. Data will be entered into the NCI CCR C3D database.

All AEs, including clinically significant abnormal findings on laboratory evaluations, regardless of severity, will be followed until return to baseline or stabilization of event. Patients will be followed for AEs from the time the patient receives the first mRNA vaccine dose to the time of the second follow-up evaluation, or until off-study, whichever comes first.

An abnormal laboratory value will be recorded in the database as an AE **only** if the laboratory abnormality is characterized by any of the following:

- Results in discontinuation from the study
- Is associated with clinical signs or symptoms
- Requires treatment or any other therapeutic intervention
- Is associated with death or another serious adverse event, including hospitalization
- Is judged by the investigator to be of significant clinical impact
- If any abnormal laboratory result is considered clinically significant, the investigator will provide details about the action taken with respect to the test drug and about the patient's outcome.

All AEs must be recorded on the AE case report form unless otherwise noted below in Section **6.1.1**.

End of study procedures: Data will be stored according to HHS and FDA regulations, and NIH Intramural Records Retention Schedule as applicable.

Loss or destruction of data: Should we become aware that a major breach in our plan to protect subject confidentiality and trial data has occurred, the NIH Intramural IRB will be notified.

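### Laboratory shifts that are asymptomatic, untreated and not judged significant have no assured place in the planned safety summaries

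*Combined protocol and SAP*

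**What the plan says.** Safety is one of the two primary objectives (1.1.1).

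**Collection.** CBC with differential and a chemistry panel are taken within 7 days before Day 0 (3.4.1), within 2 days before each of doses 2 to 4 (3.5.1), at the first follow-up evaluation (3.6.1) and at each later one (3.6.2).

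**Recording.** Section 6.1 collects AEs "from the time the patient receives the first mRNA vaccine dose to the time of the second follow-up evaluation", or until off-study if that is earlier. An abnormal laboratory value enters the database as an AE only "if the laboratory abnormality is characterized by any of the following". The conditions are discontinuation from the study, signs or symptoms, treatment, association with death or another SAE, and a final discretionary one: "Is judged by the investigator to be of significant clinical impact". None is a CTCAE grade. Section 6.4 adopts CTCAE v5.0 for AE reporting.

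**Analysis.** Section 8.4.4 says "Safety will be monitored by identifying the type and severity of any adverse events" and adds the DLT fraction per dose level with the number and grade of each DLT type. Section 8.4.2 tabulates Phase I toxicities by grade and type per dose level; its Phase II paragraph names only response. No part of 8.4.1 to 8.4.7 mentions laboratory values, change from baseline or worst laboratory grade.

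**Routes for more serious changes.** DLTs are "All grade 3 or greater toxicities related to the mRNA vaccine", with listed exceptions, and their evaluation "will occur during the 21 days after the first vaccination for each patient". Section 3.8.1 takes patients off treatment for "Grade 3 or 4 toxicity due to the vaccine", with listed exceptions.

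**The concern.** The planned safety summaries are built from AE, toxicity and DLT records, while the rule that turns a laboratory value into an AE record rests on clinical consequence or the investigator's opinion. A measured shift that causes no symptoms, needs no treatment and is not judged significant can be in the database and still appear in no planned table.

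This matters because mild shifts are the kind the protocol itself anticipates. Sections 1.2.9 and 11.2.1 associate mild hematology and chemistry abnormalities with intramuscular vaccines as a class. The rat study of the similar product (1.2.4) found raised white cells, driven mainly by neutrophils, and lower lymphocytes, with no change in serum chemistry. Whether a mild shift in a patient is counted then depends on judgement by an investigator who knows the treatment. The published safety results could understate laboratory effects even though the data to show them exist.

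**Working it through.** The plan states no figure on this point, so the check follows one kind of value through the text: an abnormal CBC or chemistry result that is asymptomatic, untreated, not linked to death or an SAE, not a cause of discontinuation, and not judged significant.

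1. **Is it measured?** Yes, at baseline, before doses 2 to 4 and at each follow-up evaluation (3.4.1, 3.5.1, 3.6.1, 3.6.2).

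2. **Does it become an AE record?** Not under 6.1, because it meets none of the conditions. Section 7.1.1 gives a laboratory finding as an example of an AE, and 6.1.1 says nothing is excluded from routine recording. Section 6.1 is the specific rule for laboratory values, however, and it is worded as a restriction. The broader texts do not displace it.

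3. **Does it reach 8.4.4 as an AE?** No, by step 2.

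4. **Does it reach 8.4.2 as a toxicity?** The plan does not define toxicity separately from AE.
   - If toxicities are recorded AEs, which the CTCAE wording in 6.4 suggests, the answer is no in both phases.
   - If toxicities include every graded laboratory value, Phase I is covered. Phase II is not, because that paragraph of 8.4.2 names only response and safety falls back on 8.4.4.

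5. **Does it reach 8.4.4 as a DLT?** Only if it is vaccine-related, grade 3 or higher and within the evaluation period. The exceptions include "Grade 3 metabolic laboratory abnormalities without significant clinical sequela that resolve to grade 2 or less within 7 days", which shows that laboratory values can otherwise count. A lower-grade or unattributed shift does not qualify.

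6. **Does another section summarise it?**
   - Section 3.8.1 is a treatment action, not a summary.
   - The tabular reports in 7.2.2 and the quarterly listings in 7.4 are built on adverse events.
   - Section 5.4 lists lymphocyte subsets as an optional immune correlate, not a safety summary.

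Such a value therefore has no assured route into the safety results. Steps 1 to 3 do not depend on when the sample was drawn: 6.1 applies the same conditions throughout the AE window.

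**How precise the missing table would be.** If no patient among n shows a given shift, the one-sided 95% upper bound on its rate is 1 − 0.05^(1/n).

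- Full Phase II cohort with the allowed inevaluable patients (8.2): n = 21 + 2 = 23, so 1 − 0.05^(1/23) = 0.122, or 12.2%.
- A cohort stopped after its first stage: n = 12, so 1 − 0.05^(1/12) = 0.221, or 22.1%.

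These bounds describe what the table could exclude. They do not estimate how often shifts occur.

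**The case against.** The strongest reply is that these values are left out by design. Section 6.1 states its rule openly and applies it to every patient, and what it leaves out had no clinical consequence by the investigator's account. Low grade alone is no bar: 6.1 follows clinically significant laboratory findings whatever their severity. Safety review also goes beyond 8.4, with weekly team discussion of each patient (7.6.1), the tabular reports in 7.2.2 and the listings in 7.4. Section 8 is brief, and its silence does not prove that laboratory values will go unreported.

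Much of this stands. It shows that important changes are likely to be seen, and it keeps the point small. It does not supply a summary of laboratory values, since the reports in 7.2.2 and 7.4 are built on events, and it leaves the counting of mild shifts to unblinded judgement on a primary objective.

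A second reply is that the remedy is weak. At nominal timing, on-treatment samples are drawn 12 to 14 days after the previous dose (14 − 2 = 12), and the rat changes had fully or partially resolved by the end of a 14-day recovery period. In refractory metastatic disease without a control arm, disease effects will also appear. Both limits are real and should be printed with the table.

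Two stronger readings are tempting. A reader might infer that serious laboratory toxicity could go unreported, or that dose escalation is compromised. The DLT definition and 3.8.1 cover vaccine-related grade 3 or higher changes, the latter with no 21-day limit, so the documents do not support this. A reader might also take the share of panels drawn after the 21-day DLT period as the size of the gap. That share does not measure it, because the 6.1 conditions are the same before and after Day 21 and lower-grade shifts are not DLTs at any time.

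**Conclusion.** The point holds as a modest descriptive gap. Asymptomatic, untreated laboratory shifts that the investigator does not judge significant, mainly lower-grade or unattributed ones, have no assured place in the safety results at any time on study, although the values are collected and safety is a primary objective.

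The conclusion assumes that 6.1 is applied as written and that toxicity in 8.4.2 means recorded AEs. On the broader reading of toxicity, the gap closes in Phase I and remains in Phase II. The number of patients affected cannot be estimated, because the documents give no rate for such shifts. Response, error rates and dose escalation are unaffected. The change is worth making because it is cheap; nothing in the design depends on it.

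**What to change.** Add to 8.4.4, for all treated patients (8.3.1), by dose level and by Phase II cohort:

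- A shift table of baseline against worst post-baseline CTCAE v5.0 grade for each gradable CBC and chemistry analyte, computed from measured values whether or not an AE was recorded. Limit it to the AE window of 6.1, leaving out the later follow-up panels that can run to five years. Identify one-course and two-course patients, because the latter have longer to reach a worst grade.
- Median change from baseline by visit for WBC, neutrophils and lymphocytes.
- A label on both saying that shifts are not attributed to vaccine, that disease-related changes are included, and that sampling shortly before the next dose can miss brief effects, so an empty table does not exclude an early transient one.

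The cost is two or three sentences in 8.4.4 and routine programming on data already collected, with no new visits or samples. The price in interpretation is a table that mixes disease and vaccine effects and has limited precision in cohorts of this size.

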8.4.5 Intention-to-Treat Analysis

An intention-to-treat (ITT) analysis will be conducted of all patients enrolled to the study. A full CONSORT flow diagram will be included in all ITT analyses.

8.4.6 Planned Interim Analyses

As noted in Section **8.2**, results after the first stage of a Simon minimax two-stage design in each Phase II cohort will be examined to determine if the minimum number of responses has been obtained.

8.4.7 Sub-Group Analyses

There are no planned analyses based on demographic characteristics since the power to do subgroup analyses would be limited and make interpretation difficult.

9 COLLABORATIVE AGREEMENTS

9.1 MODERNATX, INC.

CTA #01051-17

Tumor specific antigens (TSAs) containing between 320 and 639 amino acids will be sent to Moderna (formerly Moderna Therapeutics, Inc.) for the manufacture of a single concatemeric mRNA construct to be formulated into a vaccine for the same cancer patient. Sequencing data will be transferred electronically via the secure, encrypted Globus file transfer system (Globus.org) under the current NCI license for this transfer software. The vaccine product and associated data will be returned to the NCI-SB.

CDA #14358-18

The following data will be transferred to Moderna: (1) raw sequencing data, including tumor DNA whole exome, tumor RNA whole transcriptome, and normal DNA whole exome sequencing data in FASTQ and/or BAM format; (2) somatic variant calling results in VCF format; (3) gene expression quantification results in plain text format; (4) patient HLA types (major alleles: HLA-A, -B, -C, -DRB1, and any other HLA class II alleles that are typed, in 4 digits resolution (e.g., HLA-A:02:01)) in plain text format; (5) a list of all neoantigens that had been tested; and, (6) a list of all neoantigens tested to be immunogenic (i.e., true positives). Moderna will compare the neoantigen ranks predicted by Moderna's algorithm with the true positive and negative data from the NCI-SB. Moderna will also perform an investigation on features that are important for neoantigens to be immunogenic.

Data will be transferred electronically via a secure encrypted Amazon Web Service S3 bucket or via the secure, encrypted Globus file transfer system (Globus.org) under the current NCI license for this transfer software. No physical specimens will be shipped under this agreement. Results from Moderna's neoantigen prediction algorithm (a prioritized list of neoantigens for each patient), and a comparison with NCI-SB's results, will be returned to the NCI-SB.

10 HUMAN SUBJECTS PROTECTIONS

10.1 RATIONALE FOR PATIENT SELECTION

Subjects from both genders and all racial/ethnic groups are eligible for this study if they meet the eligibility criteria. To date, there is no information that suggests that differences in drug metabolism or disease response would be expected in one group compared to another. Efforts will be made to extend accrual to a representative population, but in this preliminary study, a balance must be struck between patient safety considerations and limitations on the number of individuals exposed to potentially toxic and/or ineffective treatments on the one hand, and the need to explore gender and ethnic aspects of clinical research on the other hand. If differences in outcome that correlate to gender or to ethnic identity are noted, accrual may be expanded or a follow-up study may be written to investigate those differences more fully.

10.2 PARTICIPATION OF CHILDREN

Since the efficacy of this experimental procedure is unknown, it does not seem reasonable to expose children to this risk without further evidence of benefit. Should results of this study indicate efficacy in treating metastatic cancer, which is not responsive to other standard forms of therapy, future research can be conducted in the pediatric population to evaluate potential benefit in that patient population.

10.3 PARTICIPATION OF SUBJECTS UNABLE TO GIVE CONSENT

Adults unable to give consent are excluded from enrolling in the protocol. However, re-consent may be necessary and there is a possibility, though unlikely, that subjects could become decisionally impaired. For this reason and because there is a prospect of direct benefit from research participation (see Section 10.5), all subjects \geq age 18 will be offered the opportunity to fill in their wishes for research and care, and assign a substitute decision maker on the "NIH Advance Directive for Health Care and Medical Research Participation" form so that another person can make decisions about their medical care in the event that they become incapacitated or cognitively impaired during the course of the study. The PI or AI will contact the NIH Ability to Consent Assessment Team (ACAT) for evaluation as needed for the following: an independent assessment of whether an individual has the capacity to provide consent; assistance in identifying and assessing an appropriate surrogate when indicated; and/or an assessment of the capacity to appoint a surrogate. For those subjects that become incapacitated and do not have a pre-determined substitute decision maker, the procedures described in MAS Policy 87-4 and OHSRP SOP 14E for appointing a surrogate decision maker for adult subjects who are (a) decisionally impaired, and (b) who do not have a legal guardian or durable power of attorney, will be followed.

10.4 EVALUATION OF BENEFITS AND RISKS/DISCOMFORTS

The experimental treatment has a chance to provide clinical benefit though this is unknown. The NCI-SB has extensive experience with adoptive cell therapy (ACT) following treatment with high-dose aldesleukin, however this experimental treatment does not include the standard NCI-SB preparative regimen or high-dose aldesleukin. Although we have seen responses to prior NCI-SB ACT treatments, we do not know if this change in our process will improve patient outcome. The risks associated with ACT are substantial, including, a delay in treatment due to the need to harvest and grow the cells, a surgical procedure (possible major) to obtain tumor for

the cell product, the possibility that a cell product cannot be generated, infection due to the surgical procedure, and death. The risks in this treatment are detailed in Section 11.

10.5 RISK/BENEFIT ANALYSIS

Because all patients in this protocol have metastatic or recurrent/refractory locally advanced cancer and limited life expectancies the potential benefit is thought to outweigh the potential risks. The risk/benefit analysis for adults with the capacity to consent, as well as for adults who may become unable to provide consent, is greater than minimal risk because the study treatment may be associated with severe side effects, with the prospect of direct benefit because the treatment may reduce the cancer burden.

10.6 CONSENT PROCESS AND DOCUMENTATION

Patients are initially consented on protocols 99-C-0128 and 03-C-0277. If the patient meets the thorough screening for eligibility, the patient, with family members or friends at the request of the patient, will be presented with the informed consent document for this protocol, who is requested to review it and to ask questions prior to agreeing to participate. The specific requirements, objectives, and potential advantages and disadvantages will be presented to the patient. The patient is reassured that participation on trial is entirely voluntary and that he/she can withdraw or decide against treatment at any time without adverse consequences. The PI, AI, or clinical fellow is responsible for obtaining written consent from the patient.

10.6.1 Telephone Consent for Part One Registration

Because many patients will have previously been treated on another NCI-SB protocol prior to beginning treatment on this protocol, these patients may not be onsite at the NIH Clinical Center in order to sign the informed consent document for this protocol. In these circumstances, in order to complete Part One of the registration procedure (see Section 2.3.2), the informed consent process and a detailed description of the protocol treatment will be discussed with the potential participant via phone.

The informed consent document will be sent to the subject. An explanation of the study will be provided over the telephone after the subject has had the opportunity to read the consent form. The subject will sign and date the informed consent. A witness to the subject's signature will sign and date the consent.

The original informed consent document will be sent back to the consenting investigator who will sign and date the consent form with the date the consent was obtained via telephone.

A fully executed copy of the informed consent will be returned via mail to the subject.

The informed consent process will be documented on a progress note by the consenting investigator.

10.6.2 Informed Consent of Non-English Speaking Subjects

If there is an unexpected enrollment of a research participant for whom there is no translated extant NIH Intramural IRB-approved consent document, the PI and/or those authorized to obtain informed consent will use the Short Form Oral Consent Process as described in MAS Policy M77-2, OHSRP SOP 12, 45 CFR 46.117 (b) (2), and 21 CFR 50.27 (b) (2). The summary that will be used is the English version of the extant NIH Intramural IRB-approved consent document. Signed copies of both the English version of the consent and the translated short form

will be given to the subject or their legally authorized representative and the signed original will be filed in the medical record.

Unless the PI is fluent in the prospective subject's language, an interpreter will be present to facilitate the conversation (using either the long-translated form or the short form). Preferably someone who is independent of the subject (i.e., not a family member) will assist in presenting information and obtaining consent. Whenever possible, interpreters will be provided copies of the relevant consent documents well before the consent conversation with the subject (24-48 hours if possible).

We request prospective NIH Intramural IRB approval of the use of the short form process for non-English speaking subjects and will notify the NIH Intramural IRB at the time of continuing review of the frequency of the use of the Short Form.

